7.6. Treatment Compliance

Every attempt will be made to select patients who have the ability to understand and comply with study instructions. The investigator is responsible for discussing methods to ensure high treatment compliance with the patient before randomization.

Randomized patients will record the date and time of administration of investigational product in a Study Drug Administration Log throughout their participation in the study. The data from the Study Drug Administration Log must be transcribed into the eCRF by site personnel.

Patient compliance with study medication will be assessed at each visit. Compliance will be assessed by review of the Study Drug Administration Log, return of empty investigational product packaging, and/or direct questioning.

The patient should be instructed to retain all empty study drug packaging after using up the medication and to bring the empty packaging and any unused medication to the study site at each visit, so that the site staff can record the amount of medication used since the last visit. Deviation(s) from the prescribed dosage regimen should be documented.

If a patient is noncompliant with study procedures and/or study drug administration, the investigator should assess the patient to determine the reason for noncompliance and educate and/or manage the patient as appropriate to improve compliance. If, in consultation with Lilly or its designee, the noncompliance is deemed to be significant or if further noncompliance occurs, the patient should be discontinued from the study (see Section 10.3.2.4 Treatment Compliance).

In some circumstances, it may be necessary to temporarily interrupt treatment (see Section 8.1.2 and Section 9.4.5). Any necessary interruption of treatment should be considered when determining noncompliance.

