10.3.2.4. Treatment Compliance

Treatment compliance with investigational product will be summarized for patients who enter Period 2. A patient will be considered compliant overall to ixekizumab or adalimumab if he/she is missing no more than 20% of the expected doses, does not miss 2 consecutive doses, and does not double-dose (that is, take more injections at the same time point than specified in the protocol). Proportions of patients compliant by visit and overall will be compared between treatment groups during Period 2 using Fisher's exact test.

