6.10. Treatment Compliance

Study treatment dispensed will be listed (including the CT Lot number) for all entered patients. Study treatment administration and compliance will be listed for all entered patients.

Patients will record information in a Study Drug Administration Log (captured in the *Exposure* eCRF page), including the date, time, and anatomical location of administration of investigational product, syringe number, who administered the investigational product, and the reason if the investigational product was not fully administered.

Treatment compliance (%) for each patient will be calculated as:

$$100 \times \frac{\text{Total number of injections administered}}{\text{Total number of injections prescribed}}$$

- Number of injections prescribed (that is, expected) is 17 injections for patients on ixekizumab with moderate-to-severe plaque psoriasis. Patients will receive 2 ixekizumab 80 mg injections at Week 0, 1 ixekizumab 80 mg injection every 2 weeks from Week 2 to Week 12, and 1 ixekizumab 80 mg injection every 4 weeks from Week 16 to Week 48.

- Number of injections prescribed (that is, expected) is 14 injections for patients on ixekizumab without moderate-to-severe plaque psoriasis. Patients will receive 2 ixekizumab 80 mg injections at Week 0 and 1 ixekizumab 80 mg injection every 4 weeks from Week 4 to Week 48.
- Number of injections prescribed (that is, expected) is 28 injections for patients on adalimumab with moderate-to-severe plaque psoriasis. Patients will receive 2 adalimumab 40 mg injections at Week 0 and 1 adalimumab 40 mg injection every 2 weeks from Week 1 to Week 51.
- Number of injections prescribed (that is, expected) is 26 injections for patients on adalimumab without moderate-to-severe plaque psoriasis. Patients will receive 1 adalimumab 40 mg injection every 2 weeks from Week 0 to Week 50.
- For patients who discontinue during Period 2, the number of injections prescribed can be derived from the IWRS study drug dispense dataset.
- The total number of injections administered will be derived using the response to the question, “Was dose administered?” on the *Exposure* eCRF page.

Overall compliance for the Open-Label Treatment Period will be considered if the patient misses no more than 20% of the expected doses, does not miss 2 consecutive doses, and does not overdose (that is, take more injections at the same time point than specified in the protocol) within the study period.

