6.17. Protocol Violations

Protocol deviations will be identified throughout the study. Important protocol deviations are defined as those violations from the protocol likely to have a significant impact on the completeness, accuracy, and/or reliability of the study data or that may significantly affect a subject's rights, safety, or well-being.

[Table RHCF.6.9](#) includes the categories and subcategories of important protocol violations, the source of identification for the violation, and the statistical programming guidance for the CSR.

A by-patient listing of important protocol deviations will be provided for all entered patients.

The number and percentage of patients having important protocol violation(s) will be summarized within category and subcategory of violations by treatment group for the following:

- Open-Label Treatment Period (ITT Population)

Additional analyses will be conducted on patients who don't have any or a subset of protocol violations for primary and/or major secondary endpoints.

Table RHCF.6.9. Identification and Action of Important Protocol Violations

Important Protocol Violation Category/Subcategory	Source to Identify Protocol Violation	Statistical Programming Guidance for Clinical Study Report
Category: Informed Consent		
Sub-Category: Informed Consent not Obtained/Missing/Late	Monitor and Stats	Either from monitor’s list, or, If patient informed consent date is after Visit 1 date or missing informed consent
Subcategory: Improper Informed Consent	Monitor	Monitor’s list
Category: Eligibility		
[1] Age <18 years	Monitor	Monitor’s list
[1a] Male patients disagree to use a reliable method of birth control during the study.	Monitor	Monitor’s list: male patients who disagree to use a reliable method of birth control during the study.
[1b] Pregnancy confirmation at Visit 1 and prior to randomization at Visit 2.	Monitor	Monitor’s list: positive pregnancy test result from lab test at Visit 1, and check if patient was randomized and takes drug. Check Visit 2 urine pregnancy test.
[1b] Are women ≥40 and <60 years of age who have had a cessation of menses for at least 12 months, and FSH <40 mIU/mL	Monitor and Stats	Monitor’s list: Women ≥40 and <60 years of age who do not have negative bHCG results and who have a FSH <40 mIU/mL at Visit 1.

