Had unqualified site personnel perform clinical safety and/or efficacy assessments	Monitor	Monitor's list
Unblinding of the blinded rater at the site	Monitor	Monitor's list

Category: Investigational Product		
Sub-Category: Treatment Assignment/Randomization Error		
Took incorrect study medication	Monitor and Stats	Monitor's list; or If IWRS study drug dispense data not match with the treatment label identifier on the Exposure as Collected eCRF page
Sub-Category: Compliance	Monitor and Stats	Monitor's list; or If non-compliant with study medication regimen or over-dose during the treatment period. Note: Non-compliance with therapy is defined to be missing more than 20% of expected doses and missing 2 or more consecutive doses; over-dose is defined as to take more injections at the same time point than specified in the protocol.
Sub-Category: Patient took medication not fit for use	Monitor	Monitor's list
Sub-Category: Other		
Randomized but did not take any study medication	Monitor	Monitor's list
Sub-Category: Treatment Assignment /Randomization Error		
Stratification error leading to incorrect dosing regimen	Monitor and Stats	Monitor's list; or If IWRS stratification data does not match patients' severity of plaque psoriasis (PASI, sPGA and BSA)

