Abbreviations: AE = adverse event; ACR = America College of Rheumatology; ALT = alanine aminotransferase; AST = aspartate aminotransferase; ATC = anatomical therapeutic chemical; BCG = Bacille de Calmette et Guérin; bDMARD = biologic disease-modifying antirheumatic drug; bHCG = beta-human chorionic gonadotropin; BP = blood pressure; BSA = body surface area; CASPAR = classification for psoriatic arthritis; CRF = case report form; C-SSRS = Columbia Suicide Severity Rating Scale; csDMARD = conventional synthetic disease-modifying antirheumatic drug; CVA = cerebrovascular accident; DNA = deoxyribonucleic acid; ECG = electrocardiogram; eCRF = electronic case report form; FSH = follicle-stimulating hormone; GCP = good clinical practice; HCV = hepatitis C virus; HIV= human immunodeficiency virus; IL = interleukin; IV = intravenous; IWRS = interactive web-response system; JAK = Janus kinase; MI = myocardial infarction; MTX = methotrexate; NSAID = nonsteroidal anti-inflammatory drug; NYHA = New York Heart Association; PASI = Psoriasis Area and Severity Index; Ps = psoriasis; PsA = psoriatic arthritis; PUVA = psoralen ultraviolet A; SAE = serious adverse event; SC = subcutaneous; SJC = swollen joint count; TB = tuberculosis; TJC = tender joint count; TNF = tumor necrosis factor; ULN = upper limit of normal; UVB = ultraviolet B; WBC = white blood cell; WHO = World Health Organization.

The term “Monitor” indicates the protocol deviation will be identified by site monitors and entered into monitor’s list using a spreadsheet. The spreadsheet will be exported as Study Data Tabulation Model (SDTM) DV domain.

The term “Stats” indicates the protocol violation will be programmed based on data in clinical database by statistical programmers with the statistical programming guidance provided as the last column. The detailed programming specification will be documented in Analysis Data Model (ADaM) specification.

The terms “Monitor and Stats” indicates the protocol deviation will be a combination of monitor’s list (SDTM.DV domain) and statistical programming from clinical database, the deviation will show if either source identifies.

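### The programming note in SAP Table RHCF.6.9 requires both missed-dose conditions for non-compliance, while SAP 6.10 and Protocol 10.3.2.4 require only one

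*SAP*

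**What the plan says.** SAP 6.10 calls a patient compliant over the Open-Label Treatment Period "if the patient misses no more than 20% of the expected doses, does not miss 2 consecutive doses, and does not overdose". Protocol 10.3.2.4 gives the same three-part rule: "missing no more than 20% of the expected doses, does not miss 2 consecutive doses, and does not double-dose". Protocol 7.6 and 8.1.1 both point to 10.3.2.4 when they discuss non-compliance.

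The compliance row of SAP Table RHCF.6.9 (Section 6.17) has a programming-guidance note that defines the same term differently: "Non-compliance with therapy is defined to be missing more than 20% of expected doses and missing 2 or more consecutive doses". Overdose is a separate trigger in that row, joined by *or*.

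The row draws on both the monitor's list and statistical programming, and the table footnote says "the deviation will show if either source identifies". The footnote adds: "The detailed programming specification will be documented in Analysis Data Model (ADaM) specification".

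SAP 6.17 uses the violations in a summary table for the ITT population. It also plans additional analyses in patients who do not "have any or a subset of protocol violations for primary and/or major secondary endpoints".

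On interruptions, Protocol 7.6 says "Any necessary interruption of treatment should be considered when determining noncompliance". Neither SAP 6.10 nor the Table RHCF.6.9 note carries this over.

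**The concern.** One term has two definitions in the same SAP, and they classify some patients differently. A patient who fails exactly one missed-dose condition is non-compliant in the 6.10 summary but not under the programmed violation rule. If the monitor's list does not pick that patient up, the violation table omits them and a violation-free analysis that uses the compliance flag retains them.

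The SAP defines no per-protocol population (6.1.3), and noninferiority on ACR50 is tested on the ITT population (6.7). The 6.17 analyses are therefore the only planned look at the primary and major secondary endpoints with violators removed. Keeping poorly adherent patients in them weakens that check, most obviously for the noninferiority claim.

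**Working it through.** **Reproducing the plan's counts.** SAP 6.10 gives expected injections over 52 weeks. Counting its dosing weeks, with two injections at Week 0 where the starting dose needs two:

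- Ixekizumab Q2W/Q4W: 2 + 6 (Weeks 2 to 12) + 9 (Weeks 16 to 48) = 17
- Ixekizumab Q4W: 2 + 12 = 14
- Adalimumab, moderate-to-severe psoriasis: 2 + 26 = 28
- Adalimumab, others ("1 adalimumab 40 mg injection every 2 weeks from Week 0 to Week 50"): 26

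All four match the SAP. With Week 0 counted as one occasion, the dosing occasions are 16, 13, 27 and 26.

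**Logic.** Let A be no more than 20% of doses missed, and B be no two consecutive doses missed. On missed doses, SAP 6.10 defines compliant as A and B, so non-compliant is (not A) or (not B). The table note defines non-compliant as (not A) and (not B). The two rules disagree whenever exactly one condition fails.

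**Full 52 weeks** (Week 0 dose taken as given; share = missed occasions / scheduled occasions):

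| Regimen | Two consecutive misses only | Every second dose missed | Fewest misses above 20% |
|---|---|---|---|
| Ixekizumab Q4W | 2/13 = 15.4% | 6/13 = 46.2% | 3 (23.1%) |
| Ixekizumab Q2W/Q4W | 2/16 = 12.5% | 8/16 = 50.0% | 4 (25.0%) |
| Adalimumab | 2/26 = 7.7% | 13/26 = 50.0% | 6 (23.1%) |
| Adalimumab, moderate-to-severe | 2/27 = 7.4% | 13/27 = 48.1% | 6 (22.2%) |

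Every pattern in the two middle columns is non-compliant under 6.10 and unflagged by the note. The first never exceeds 20%; the second never has two misses in a row. Using injections (14, 17, 26, 28) as denominators gives 14.3%, 11.8%, 7.7% and 7.1% for two consecutive misses, and the same minimum counts of 3, 4, 6 and 6.

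**Week 24.** The primary and major secondary endpoints are assessed at the Week 24 lock (SAP 6.18). The SAP gives no expected count for patients still on treatment at that cut. I assume doses scheduled before Week 24 in Protocol Table RHCF.2.1, and show the effect of adding the Week 24 dose where one is scheduled:

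| Regimen | Two consecutive misses, before Week 24 | With Week 24 dose | Every second dose missed, before Week 24 |
|---|---|---|---|
| Ixekizumab Q4W | 2/6 = 33% (flagged) | 2/7 = 29% (flagged) | 3/6 = 50% |
| Ixekizumab Q2W/Q4W | 2/9 = 22% (flagged) | 2/10 = 20% (not flagged) | 4/9 = 44% |
| Adalimumab | 2/12 = 17% (not flagged) | 2/13 = 15% (not flagged) | 6/12 = 50% |
| Adalimumab, moderate-to-severe | 2/13 = 15% (not flagged) | none scheduled | 6/13 = 46% |

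At this horizon the same lapse can be a violation on ixekizumab and not on adalimumab. Missing every second dose stays unflagged throughout. The Q2W/Q4W result also depends on the unit: counted in injections before Week 24, 2/10 = 20% is not flagged.

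**The case against.** The strongest reply is that a narrower rule may be intended. SAP 6.17 limits the table to important deviations, and 6.10 serves a descriptive summary. The revision history says the table was updated from a Trial Issue Management Plan that the reader does not have. Protocol 7.6 and 8.1.1 also speak of non-compliance deemed significant. This makes an intended difference possible, but none of it states a different threshold. The note defines non-compliance itself, not a severe grade of it. A rule that passes a patient who misses about half of all doses is also hard to read as a deliberate threshold for importance.

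Three limits stand:

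- The monitor's list is an independent source and may catch these patients. The ADaM specification is still to come, though it should implement the SAP and not silently correct it.
- The subset of violations in 6.17 is undefined, so the compliance flag may not drive every violation-free analysis.
- A bare *or* in the note would list interruptions that the protocol itself directs, such as those around surgery in Protocol 8.1.2, as important violations. SAP 6.10 as written already counts these as non-compliance when two consecutive doses are missed.

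A reader might also infer that two consecutive misses never trigger the flag in any regimen. That holds for the 52-week denominator only; on ixekizumab Q4W they do trigger it at Week 24.

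**Conclusion.** The inconsistency is real, and the note is wrong as written against SAP 6.10 and Protocol 10.3.2.4. It affects the programmed part of the important-violation table and any 6.17 violation-free analysis that uses the compliance flag.

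Over 52 weeks, two consecutive misses alone (7% to 15% of occasions) are never flagged. At Week 24, on the assumed count of doses before that week, they are flagged on ixekizumab (33% and 22%) and not on adalimumab (17% and 15%). The Q2W/Q4W result is borderline and reverses if the Week 24 dose is counted. Alternate-dose missing is unflagged in every regimen at both horizons.

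A reader might infer that the confirmatory results are at risk, or that the rule was built to favour one arm. The documents support neither. The primary and major secondary tests are on the ITT population and do not use the flag, and the arm difference follows only from the different dosing intervals. The documents give no missed-dose rate, so the number of patients affected cannot be stated.

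**What to change.** In the Table RHCF.6.9 note, replace *and* with *or* between the two missed-dose conditions, or replace the note with a cross-reference to SAP 6.10, so that one definition serves both places. Carry it into the ADaM specification.

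If necessary interruptions are to be considered, as Protocol 7.6 says, state this once in SAP 6.10 and let the table inherit it. Adding it to the table note alone would make the two sections differ again.

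The cost is a wording change. The violation-free set may become smaller and its confidence interval wider, by an amount that cannot be given without a missed-dose rate. The ITT tests do not change.

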6.18. Interim Analyses and Data Monitoring

An interim database lock will occur, and the analysis will be performed at the time (that is, a cutoff date) when the last patient completes Visit 8 (Week 24), completes ETV, or discontinues from Period 2. This database lock will include all data collected by the cutoff date including data after Week 24 from the Open-Label Treatment Period and follow-up data from patients who have begun Post-Treatment Follow-Up Period (Period 3).

This interim database lock at Week 24 will be considered the primary database lock for this study because all primary and major secondary study objectives will be assessed at this time.

A final database lock will occur after all enrolled patients have completed or discontinued the Post-Treatment Follow-Up Period.

There will be no data monitoring committee.

6.19. Clinical Trial Registry Analyses

Additional analyses will be performed for the purpose of fulfilling the Clinical Trial Registry (CTR) requirements.

Analyses provided for the CTR requirements include the following:

Summary of adverse events, provided as a dataset which will be converted to an XML file. Both Serious Adverse Events and “Other” Adverse Events are summarized: by treatment group, by MedDRA PT.

- An adverse event is considered “Serious” whether or not it is a TEAE.
- An adverse event is considered in the “Other” category if it is both a TEAE and is not serious. For each Serious AE and “Other” AE, for each term and treatment group, the following are provided:
 - the number of participants at risk of an event
 - the number of participants who experienced each event term
 - the number of events experienced
- Consistent with www.ClinicalTrials.gov requirements, “Other” AEs that occur in fewer than 5% of patients/subjects in every treatment group may not be included if a 5% threshold is chosen (5% is the minimum threshold).
- AE reporting is consistent with other document disclosures for example, the CSR, manuscripts, and so forth.

7. References

- Coates LC, Fransen J, Helliwell PS. Defining minimal disease activity in psoriatic arthritis: a proposed objective target for treatment. *Ann Rheum Dis*. 2010a;69(1):48-53.
- Coates LC, Helliwell PS. Validation of minimal disease activity criteria for psoriatic arthritis using interventional trial data. *Arthritis Care Res (Hoboken)*. 2010b;62(7):965-969.

Appendix 1. Definition of Numbers Needed to Treat (NNT)

Numbers needed to treat (NNT) is defined as reciprocal of the difference in response rate between active treatment and comparator (Absolute Risk Reductions [ARR]). For instance, if ADA and IXE had response rates of 30% and 60%, respectively, then $NNT = 1 / (0.6 - 0.3) = 3.3$. As for the CI, we take the CI for NNT as the reciprocal of the CI for ARR. The NNT and its CI will not be reported if 0 is included in the CI for ARR, i.e. the superiority test for two treatment arms is not significant.

Reference Table: List of Topical Treatments that are Prescribed/Administered for Psoriasis or Psoriatic Arthritis Patients with Appropriate ATC Code

Topical Treatments	ATC Code

Topical corticosteroids: These powerful anti-inflammatory drugs are the most frequently prescribed medications for treating mild-to-moderate psoriasis. They slow cell turnover by suppressing the immune system, which reduces inflammation and relieves associated itching. Topical corticosteroids range in strength from mild to very strong. Low-potency corticosteroid ointments are usually recommended for sensitive areas, such as your face or skinfolds, and for treating widespread patches of damaged skin. Your doctor may prescribe stronger corticosteroid ointment for small areas of your skin, for persistent plaques on your hands or feet, or when other treatments have failed. Medicated foams and scalp solutions are available to treat psoriasis patches on the scalp. Long-term use or overuse of strong corticosteroids can cause thinning of the skin and resistance to the treatment's benefits. To minimize side effects and to increase effectiveness, topical corticosteroids are generally used on active outbreaks until they are under control.
	D07-- (Level 2)

Vitamin D analogs: These synthetic forms of vitamin D slow down the growth of skin cells. Calcipotriene (Dovonex) is a prescription cream or solution containing a vitamin D analog that may be used alone to treat mild-to-moderate psoriasis or in combination with other topical medications or phototherapy. This treatment can irritate the skin. Calcitriol (Rocaltrol) is expensive, but may be equally effective and possibly less irritating than calcipotriene.
	A11CC

Anthralin: This medication is believed to normalize DNA activity in skin cells. Anthralin (Dritho-Scalp) can also remove scale, making the skin smoother. However, anthralin can irritate skin, and it stains virtually anything it touches, including skin, clothing, countertops, and bedding. For that reason, doctors often recommend short-contact treatment – allowing the cream to stay on your skin for a brief time before washing it off. Anthralin is sometimes used in combination with ultraviolet light.
	D05AC

Topical retinoids: These are commonly used to treat acne and sun-damaged skin, but tazarotene (Tazorac, Avage) was developed specifically for the treatment of psoriasis. Like other vitamin A derivatives, it normalizes DNA activity in skin cells and may decrease inflammation. The most common side effect is skin irritation. It may also increase sensitivity to sunlight, so sunscreen should be applied while using the medication. Although the risk of birth defects is far lower for topical retinoids than for oral retinoids, your doctor needs to know if you are pregnant or intend to become pregnant if you are using tazarotene.
	D05BB

Calcineurin inhibitors: Currently, calcineurin inhibitors – tacrolimus (Prograf) and pimecrolimus (Elidel) – are approved only for the treatment of atopic dermatitis, but studies have shown them to be effective, at times, in the treatment of psoriasis. Calcineurin inhibitors are thought to disrupt the activation of T cells, which in turn reduces inflammation and plaque buildup. The most common side effect is skin irritation. Calcineurin inhibitors are not recommended for long-term or continuous use because of a potential increased risk of skin cancer and lymphoma. Calcineurin inhibitors are used only with your doctor's input and approval. They may be especially helpful in areas of thin skin, such as around the eyes, where steroid creams or retinoids are too irritating or may cause harmful effects.
	L04AD

Salicylic acid: Available over-the-counter (nonprescription) and by prescription, salicylic acid promotes sloughing of dead skin cells, and reduces scaling. Sometimes it is combined with other medications, such as topical corticosteroids or coal tar, to increase its effectiveness. Salicylic acid is available in medicated shampoos and scalp solutions to treat scalp psoriasis.
	D02AF

Coal tar: A thick, black byproduct of the manufacture of petroleum products and coal, coal tar is probably the oldest treatment for psoriasis. It reduces scaling, itching, and inflammation. Exactly how it works is not known. Coal tar has few known side effects, but it is messy, stains clothing and bedding, and has a strong odor. Coal tar is available in over-the-counter shampoos, creams, and oils. It is also available in higher concentrations by prescription.
	D05AA

Topical Treatments	ATC Code
Moisturizers: By themselves, moisturizing creams will not heal psoriasis, but they can reduce itching and scaling and can help combat the dryness that results from other therapies. Moisturizers in an ointment base are usually more effective than are lighter creams and lotions.	D02A- (Level 3)
Calcipotriene	D05AX
Tazarotene	D05AX
Herbal and traditional preparations	V90

Note: ATC = WHOCC Anatomical Therapeutic Chemical classification system; WHOCC = World Health Organization Collaborating Centre for Drug Statistics Methodology.

